### Vital Signs

Vital signs data will be summarized using descriptive statistics (mean, standard deviation, median, quartiles, minimum, and maximum) of actual values and change from baseline for each nominal visit over time (ie, unscheduled assessments will be excluded).

#### **Electrocardiograms**

All ECGs obtained during the study will be evaluated for safety. The triplicate pre-dose data will be averaged. Summary statistics and data presentations for pre-dose will use the averaged data. Any data obtained from ECGs repeated for safety reasons after the nominal time points will not be averaged along with the preceding.

QT intervals will be corrected for heart rate using standard correction factors (ie, Fridericia's [default correction], Bazett's [if necessary], and possibly a study-specific factor, as appropriate). However, safety assessments as to QTc prolongation will be based on the Fridericia's correction formula. Data will be summarized and listed for QT, HR, RR, PR, QRS, QTc.

Descriptive statistics (n, mean, median, standard deviation, minimum, and maximum) of QTc and other ECG parameters will be used to summarize absolute values and changes from baseline on treatment. Categorical analysis will be conducted for the maximum change from baseline in corrected QT, PR, and QRS and the maximum post-baseline corrected QT interval.

### **10. QUALITY CONTROL AND QUALITY ASSURANCE**

During study conduct, Pfizer or its agent will conduct periodic monitoring visits to ensure that the protocol and Good Clinical Practices (GCPs) are being followed. The monitors may review source documents to confirm that the data recorded on CRFs is accurate. The investigator and institution will allow Pfizer monitors/auditors or its agents and appropriate regulatory authorities direct access to source documents to perform this verification.

The study site may be subject to review by the Institutional Review Board (IRB)/Ethics Committee (EC), and/or to quality assurance audits performed by Pfizer, or companies working with or on behalf of Pfizer, and/or to inspection by appropriate regulatory authorities.

It is important that the investigator(s) and their relevant personnel are available during the monitoring visits and possible audits or inspections and that sufficient time is devoted to the process.

# 11. DATA HANDLING AND RECORD KEEPING

### 11.1. Case Report Forms/Electronic Data Record

As used in this protocol, the term CRF should be understood to refer to either a paper form or an electronic data record or both, depending on the data collection method used in this study.

A CRF is required and should be completed for each included participant. The completed original CRFs are the sole property of Pfizer and should not be made available in any form to third parties, except for authorized representatives of Pfizer or appropriate regulatory authorities, without written permission from Pfizer. The investigator shall ensure that the CRFs are securely stored at the study site in encrypted electronic form and will be password protected to prevent access by unauthorized third parties.

The investigator has ultimate responsibility for the collection and reporting of all clinical, safety and laboratory data entered on the CRFs and any other data collection forms (source documents) and ensuring that they are accurate, authentic / original, attributable, complete, consistent, legible, timely (contemporaneous), enduring and available when required. The CRFs must be signed by the investigator or by an authorized staff member to attest that the data contained on the CRFs is true. Any corrections to entries made in the CRFs or source documents must be dated, initialed and explained (if necessary) and should not obscure the original entry.

In most cases, the source documents are the participant's chart in the hospital or the physician's office. In these cases, data collected on the CRFs must match the data in those charts.

# 11.2. Record Retention

To enable evaluations and/or audits from regulatory authorities or Pfizer, the investigator agrees to keep records, including the identity of all participating participants (sufficient information to link records, eg, CRFs and hospital records), all original signed informed consent documents, copies of all CRFs, safety reporting forms, source documents, and detailed records of treatment disposition, and adequate documentation of relevant correspondence (eg, letters, meeting minutes, telephone calls reports). The records should be retained by the investigator according to International Council for Harmonisation (ICH), according to local regulations, or as specified in the Clinical Study Agreement (CSA), whichever is longer. The investigator must ensure that the records continue to be stored securely for so long as they are retained.

If the investigator becomes unable for any reason to continue to retain study records for the required period (eg, retirement, relocation), Pfizer should be prospectively notified. The study records must be transferred to a designee acceptable to Pfizer, such as another investigator, another institution, or to an independent third party arranged by Pfizer. Investigator records must be kept for a minimum of 15 years after completion or discontinuation of the study or for longer if required by applicable local regulations.

The investigator must obtain Pfizer's written permission before disposing of any records, even if retention requirements have been met.

# **12. ETHICS**

### 12.1. Institutional Review Board (IRB)/Ethics Committee (EC)

It is the responsibility of the investigator to have prospective approval of the study protocol, protocol amendments, informed consent documents, and other relevant documents, eg, recruitment advertisements, if applicable, from the IRB/EC. All correspondence with the IRB/EC should be retained in the Investigator file. Copies of IRB/EC approvals should be forwarded to Pfizer.

The only circumstance in which an amendment may be initiated prior to IRB/EC approval is where the change is necessary to eliminate apparent immediate hazards to the participants. In that event, the investigator must notify the IRB/EC and Pfizer in writing immediately after the implementation.

### 12.2. Ethical Conduct of the Study

The study will be conducted in accordance with legal and regulatory requirements, as well as the general principles set forth in the International Ethical Guidelines for Biomedical Research Involving Human Subjects (Council for International Organizations of Medical Sciences 2002), Guidelines for GCP (ICH 1996), and the Declaration of Helsinki (World Medical Association 1996 & 2008) and Schedule Y, Drug and Cosmetics Act 1940 and Rules 1945.

In addition, the study will be conducted in accordance with the protocol, the ICH guideline on GCP, and applicable local India regulatory requirements and laws.

### 12.3. Participant Information and Consent

All parties will comply with all applicable laws, including laws regarding the implementation of organizational and technical measures to ensure protection of participant personal data. Such measures will include omitting participant names or other directly identifiable data in any reports, publications, or other disclosures, except where required by applicable laws.

The personal data will be stored at the study site in encrypted electronic form and will be password protected to ensure that only authorized study staff have access. The study site will implement appropriate technical and organizational measures to ensure that the personal data can be recovered in the event of disaster. In the event of a potential personal data breach, the

study site shall be responsible for determining whether a personal data breach has in fact occurred and, if so, providing breach notifications as required by law.

To protect the rights and freedoms of natural persons with regard to the processing of personal data, when study data is compiled for transfer to Pfizer and other authorized parties, participant names, addresses, and other identifiable data will be replaced by a numerical code consisting of a numbering system provided by Pfizer in order to de-identify study participants. The study site will maintain a confidential list of participants who participated in the study linking their numerical code to the participant's actual identity. In case of data transfer, Pfizer will maintain high standards of confidentiality and protection of participant personal data consistent with applicable privacy laws.

The informed consent documents must be in compliance with ICH GCP, local regulatory requirements, and legal requirements, including applicable privacy laws.

The informed consent documents used during the informed consent process must be reviewed by the sponsor, approved by the IRB/EC before use, and available for inspection.

The investigator must ensure that each study participant, or his or her legally acceptable representative, is fully informed about the nature and objectives of the study and possible risks associated with participation.

Whenever consent is obtained from a participant's legally acceptable representative, the participant's assent (affirmative agreement) must subsequently be obtained when the participant has the capacity to provide assent, as determined by the IRB/EC. If the investigator determines that a participant's decisional capacity is so limited he/she cannot reasonably be consulted, as permitted by the IRB/EC and consistent with local regulatory and legal requirements, then the participant's assent may be waived with source documentation of the reason assent was not obtained. If the study participant does not provide consent (eg, minor, decisionally impaired adult), how the investigator determined that the person signing the consent was the participant's legally acceptable representative, the consent signer's relationship to the study participant (eg, parent, spouse) and that the participant's assent was obtained, or waived. If assent is obtained verbally it must be documented in the source documents.

The investigator, or a person designated by the investigator, will obtain written informed consent from each participant or the participant's legally acceptable representative, when applicable, before any study-specific activity is performed. The investigator will retain the original of each participant's signed consent document.

### 12.4. Participant Recruitment

Advertisements approved by ethics committees and investigator databases may be used as recruitment procedures.

PFIZER CONFIDENTIAL

### 12.5. Reporting of Safety Issues and Serious Breaches of the Protocol or ICH GCP

In the event of any prohibition or restriction imposed (ie, clinical hold) by an applicable Competent Authority in any area of the World, or if the investigator is aware of any new information which might influence the evaluation of the benefits and risks of the investigational product, Pfizer should be informed immediately.

In addition, the investigator will inform Pfizer immediately of any urgent safety measures taken by the investigator to protect the study participants against any immediate hazard, and of any serious breaches of this protocol or of ICH GCP that the investigator becomes aware of.

# **13. DEFINITION OF END OF STUDY**

### 13.1. End of Study in Participating Country

End of study in participating country is defined as 1 year after the LPFV date in the study.

At the end of study, participants who are on treatment and benefiting from lorlatinib treatment will be moved to commercially available lorlatinib (if considered appropriate by the Investigator) as soon as feasible.

# **14. SPONSOR DISCONTINUATION CRITERIA**

Premature termination of this study may occur because of a regulatory authority decision, change in opinion of the IRB/EC, drug safety problems, or at the discretion of Pfizer.

If a study is prematurely terminated or discontinued, Pfizer will promptly notify the investigator. After notification, the investigator must contact all participating participants and the hospital pharmacy (if applicable) within 7 days. As directed by Pfizer, all study materials must be collected and all CRFs completed to the greatest extent possible.

# **15. PUBLICATION OF STUDY RESULTS**

# **15.1.** Communication of Results by Pfizer

Pfizer fulfills its commitment to publicly disclose clinical trial results through posting the results of studies on www.clinicaltrials.gov (ClinicalTrials.gov), www.pfizer.com, and/or the European Clinical Trials Database (EudraCT), www.ctri.nic.in (Clinical Trials Registry-India) and other public registries in accordance with applicable local laws/regulations.

www.clinicaltrials.gov

Pfizer posts clinical trial Basic Results on www.clinicaltrials.gov for all Pfizer-sponsored interventional studies that evaluate the safety and/or efficacy of a Pfizer product.

# **15.2.** Publications by Investigators

Pfizer has no objection to publication by investigator of any information collected or generated by investigator, whether or not the results are favorable to the investigational drug.

However, to ensure against inadvertent disclosure of confidential information or unprotected inventions, investigator will provide Pfizer an opportunity to review any proposed publication or other type of disclosure before it is submitted or otherwise disclosed.

The investigator will provide manuscripts, abstracts, or the full text of any other intended disclosure (poster presentation, invited speaker or guest lecturer presentation, etc.) to Pfizer at least 30 days before they are submitted for publication or otherwise disclosed. If any patent action is required to protect intellectual property rights, the investigator agrees to delay the disclosure for a period not to exceed an additional 60 days.

The investigator will, on request, remove any previously undisclosed confidential information (other than the Study results themselves) before disclosure.

If the study is part of a multicenter study, the investigator agrees that the first publication is to be a joint publication covering all centers. However, if a joint manuscript has not been submitted for publication within 12 months of completion or termination of the study at all participating sites, investigator is free to publish separately, subject to the other requirements of this section.

For all publications relating to the study, institution will comply with recognized ethical standards concerning publications and authorship, including Section II - "Ethical Considerations in the Conduct and Reporting of Research" of the Uniform Requirements for Manuscripts Submitted to Biomedical Journals, http://www.icmje.org/index.html#authorship, established by the International Committee of Medical Journal Editors.

Publication of study results is also provided for in the Clinical Study Agreement between Pfizer and the institution. In this section entitled Publications by Investigators, the defined terms shall have the meanings given to them in the Clinical Study Agreement.

### **Appendix 1. Contraceptive Guidance**

### **Definition**

WOCBP: A woman is considered fertile following menarche and until becoming post-menopausal unless permanently sterile (see below).

If fertility is unclear (eg, amenorrhea in adolescents or athletes) and a menstrual cycle cannot be confirmed before first dose of study intervention, additional evaluation should be considered.

Women in the following categories are not considered WOCBP:

- 1. Premenarchal.
- 2. Premenopausal female with 1 of the following:
  - Documented hysterectomy;
  - Documented bilateral salpingectomy;
  - Documented bilateral oophorectomy.

For individuals with permanent infertility due to an alternate medical cause other than the above, (eg, mullerian agenesis, androgen insensitivity), Investigator discretion should be applied to determining study entry.

Note: Documentation for any of the above conditions can come from the site personnel's review of the participant's medical records, medical examination, or medical history interview. The method of documentation should be recorded in the participant's medical record for the study.

- 3. Postmenopausal female:
  - A postmenopausal state is defined as age 60 or older or no menses for 12 months without an alternative medical cause.
    - A high FSH level in the postmenopausal range may be used to confirm a postmenopausal state in women not using hormonal contraception or HRT.
  - Females on HRT and whose menopausal status is in doubt will be required to use 1 of the non-estrogen hormonal highly effective contraception methods if they wish to continue their HRT during the study. Otherwise, they must discontinue HRT to allow confirmation of postmenopausal status before study enrollment.

#### **Contraception Guidance**

#### Contraception – For Women

Female participants must use highly effective contraception while taking study intervention and for at least 6 months after stopping study intervention.

Lorlatinib may reduce the effectiveness of hormonal contraceptive methods; therefore, hormonal contraceptives may not be considered highly effective. If hormonal contraception is unavoidable, it must be used in combination with a condom.

Highly effective methods that have low user dependency includes:

- 1. Intrauterine device (IUD).
- 2. Bilateral tubal occlusion.
- 3. Vasectomized partner.
  - Vasectomized partner is a highly effective contraceptive method provided that the partner is the sole sexual partner of the WOCBP and the absence of sperm has been confirmed. If not, an additional highly effective method of contraception should be used. The spermatogenesis cycle is approximately 90 days.

#### Contraception – For Men

Male participants must use a condom while taking study intervention and for at least 3 months after stopping study intervention.

# Appendix 2. Pharmacokinetic Properties of Statins and Lipid Lowering Agents

The PK properties of statins and lipid lowering agents are provided in Table 3 and Table 4, respectively.

Table 3.         Pharmacokinetic Properties of State
--

Generic Name	Pitavastatin	Pravastatin	Rosuvastatin	Atorvastatin	Simvastatin	Lovastatin	Fluvastatin
Metabolism †	++	+	+	+++	+++	+++	+++
Metabolizing CYP enzyme	(2C9)	(3A4)	2C9 (2C19)	3A4 (2C8)	3A4 2C8	3A4 2C8	2C9
(of lactone or acid form)							
Inhibitor of CYP3A4 ‡	-	-	+	+	+	+	+
Inhibitor of CYP2C9 ‡	-	-	(+)	-	-	-	+
Triglyceride lowering effect	22%-31%**	11%-14%*	17%*	14%-19%*	10%-14%*	13%*	5%***

Adapted from Neuvonen et al, 2006.

Parentheses indicate minor significance.

†Three (3) plus signs indicate extensively metabolized, and 1 plus sign indicates limited metabolism, eliminated mainly unchanged.

‡A plus sign indicates yes, and a minus sign indicates no.

\*Baseline TG 100-200 mg/dL; Effect of Statins vs Placebo on Triglyceride Levels in 10 Primary and Secondary Placebo-Controlled Outcome Trials table in Miller 2009.

\*\*Baseline TG ≥150 mg/dL; Kajinami et al, 2003.

\*\*\*Schaefer et al, 2004.6

Abbreviations: CYP=cytochrome P450; TG=triglyceride.

		Fi	Fish Oils		
Generic Name	Nicotinic Acid	Gemfibrozil	Fenofibrate	Ethyl esters of omega-3 fatty acids	
Dose	100–2000 mg QD	600 mg BID	200 mg QD	4 gm QD/2 gm BID	
Metabolism ‡	-	-	-	-	
Metabolizing CYP enzymes	-	-	-	-	
(of lactone or acid form) ‡					
Inhibitor of CYP3A4 ‡	-	-	-	-	
Inhibitor of CYP2C9 ‡	-	+++	++	-	
Inhibitor of CYP2C19 ‡	-	++	+	-	
Inhibitor of CYP1A2 ‡	-	+	-	-	
Triglyceride lowering effect	20%-50%*	20%-50%*	36%-55% e	45%	
$(TG \ge 150 \text{ mg/dL})$					
Drug interactions	Caution should be used	Concomitant administration	May increase exposure to	-	
-	when prescribing niacin with	with statins is	pravastatin and its metabolite		
	statins	contraindicated	(13%-26%) when used		
			concomitantly		

### Table 4. Pharmacokinetic properties of Lipid Lowering Agents

‡A plus sign indicates yes, and a minus sign indicates no.

\*NCEP-ATP III, 2001.

Abbreviations: BID=twice daily; QD=once daily.

a. PI, 4/2015.

b. PI, 11/2014.

c. PI, 12/2014.

d. PI, 05/2014.

e. Primary hypertriglyceridemia – severe hypertriglyceridemia (baseline TG levels 500 to 1500 mg/dL).

### Appendix 3. RECIST Version 1.1 Tumor Assessment Criteria

At baseline, individual tumor lesions will be categorized by the Investigator as either measurable or not, according to the criteria summarized below.

1. Measurable Lesions

Lesions that can be accurately measured in at least 1 dimension (longest diameter in the plane of measurement is to be recorded) with a minimum size of:

- 10 mm for lesions other than lymph nodes and assessed by CT scan (CT scan slice thickness no greater than 5 mm);
- 10 mm for lesions assessed clinically by caliper measurement (lesions which cannot be accurately measured with calipers should be recorded as non-measurable);
- 20 mm for lesions assessed by chest X-ray;
- 15 mm in short axis for lymph nodes when assessed by CT scan (CT scan slice thickness recommended to be no greater than 5 mm).
- 2. Non-measurable Lesions

Non-measurable lesions include small lesions (longest diameter <10 mm or pathological lymph nodes with a  $\geq$ 10 but <15 mm short axis) as well as truly non-measurable lesions. Truly non-measurable lesions include leptomeningeal disease, ascites, pleural or pericardial effusion, inflammatory breast disease, lymphangitic involvement of skin or lung, abdominal masses identified by physical examination and not measurable by reproducible imaging techniques.

Nodes that have a short axis <10 mm are considered non-pathological and should not be recorded or followed.

3. Special Considerations Regarding Specific Lesions

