## 7. ASSESSMENTS

## 7.1. Antitumor Activity Assessments

Tumor assessments will include all known or suspected disease sites. Computed tomography (CT) or magnetic resonance imaging (MRI) scans of chest abdomen pelvis (CAP) and MRI of the brain will be performed at Screening. Gadolinium contrast enhanced MRI must be used for assessment of CNS lesions with contingent slices of 1 mm for lesions 5 mm to 10 mm in size, 5 mm for lesions greater than 10 mm. For all tumor assessments, the method of assessment that was used at Screening should be the same method used throughout the study. CT and MRI scans to be done at every 12 weeks  $\pm 1$  week till the end of treatment. Tumor assessment should be repeated at the end of treatment if more than 6 weeks have passed since the last evaluation. Moreover, radiological tumor assessments will be conducted whenever disease progression is suspected (eg, symptomatic deterioration).

Assessment of response will be made using RECIST version 1.1 (Appendix 3). Confirmation of response will be required at least 4 weeks after initial response is observed.

All participants' files and radiologic images must be available for source verification.

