### **Recording Tumor Measurements**

All measurable lesions up to a maximum of 2 lesions per organ and up to 5 in total and representative of all involved organs should be identified as target lesions and measured and recorded at baseline and at the stipulated intervals during treatment. Target lesions should be selected on the basis of their size (lesions with the longest diameters) and their suitability for accurate repetitive measurements (either by imaging techniques or clinically).

The longest diameter will be recorded for each target lesion. The sum of the longest diameter of all target lesions will be calculated and recorded as the baseline sum diameter to be used as reference to further characterize the objective tumor response of the measurable dimension of the disease during treatment.

One (1) exception to the above described approach is related to pathological lymph nodes. Pathological lymph nodes are defined as measurable lesions and may be identified as target lesions if the criterion of a short axis of  $\geq 15$  mm by CT scan is met. Only the short axis of these nodes will contribute to the baseline sum. Nodal size is normally reported as 2 dimensions in the plane in which the image is obtained (for CT scan this is almost always the axial plane; for MRI the plane of acquisition may be axial, sagittal or coronal). The smaller of these measures is the short axis.

A sum of the diameters (longest for non-nodal lesions, short axis for nodal lesions) for all target lesions will be calculated and reported as the baseline sum diameters. The baseline sum diameters will be used as reference to further characterize any objective tumor regression in the measurable dimension of the disease.

All other lesions (or sites of disease) should be identified as non-target lesions and should also be recorded at baseline. Measurements are not required and these lesions should be followed as "present", "absent", or in rare cases "unequivocal progression". In addition, it is possible to record multiple non-target lesions involving the same organ as a single item on the CRF (eg, "multiple enlarged pelvic lymph nodes" or "multiple liver metastases").

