#### **Definition of Tumor Response**

#### Target Lesions

Response in target lesions is defined as follows:

- CR: disappearance of all target lesions.
- PR: at least a 30% decrease in the sum of diameters of target lesions, taking as reference the baseline sum diameters.
- PD: at least a 20% increase in the sum of diameters of target lesions, taking as reference the smallest sum on study (this includes the baseline sum if that is the smallest on study). In addition to the relative increase of 20%, the sum must also demonstrate an absolute increase of at least 5 mm. The appearance of 1 or more new lesions is also considered a sign of progression.
- Stable disease (SD): neither sufficient shrinkage to qualify for PR nor sufficient increase to qualify for PD, taking as reference the smallest sum diameters while on study.

When nodal disease is included in the sum of target lesions and the nodes decrease to "normal" size (<10 mm), they may still have a measurement reported on scans. This measurement should be recorded even though the nodes are normal in order not to overstate progression should it be based on increase in size of the nodes. As noted earlier, this means that patients with CR may not have a total sum of "0" on the CRF.

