#### Non-Target Lesions

While some non-target lesions may actually be measurable, they need not be measured and instead should be assessed only qualitatively at the time points specified in the protocol.

Response in non-target lesions is defined as follows:

• CR: disappearance of all non-target lesions and normalization of tumor marker level. All lymph nodes must be non-pathological in size (<10 mm short axis).

- Non-CR/Non-PD: persistence of one or more non-target lesion(s) and/or maintenance of tumor marker level above the normal limits.
- PD: unequivocal progression of existing non-target lesions. (Note: the appearance of one or more new lesions is also considered progression).

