5.2.5. Measurable Disease

A participant will be considered to have measurable disease if there is at least one target lesion identified at baseline meeting the following criteria:

- Non lymph node lesions with longest diameter ≥ 10 mm by Computerized Tomography (CT) scan,
- Non lymph node lesions with longest diameter ≥ 10 mm caliper measurement by clinical exam,
- CNS lesions with longest diameter ≥5 mm provided by gadolinium contrast enhanced Magnetic Resonance Imaging (MRI) performed with contingent slices of 1 mm, or

• Lymph nodes with short axis ≥ 15 mm when assessed by CT.

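### Protocol Appendix 3 conflicts with Protocol 7.1 and SAP 5.2.5 on brain lesions of 5 mm to under 10 mm; a participant left with no intracranial target lesion cannot have an intracranial PR but still counts in the IC-ORR denominator

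*Protocol*

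**What the plan says.** Protocol 7.1 refers response assessment to Appendix 3, where the investigator sorts baseline lesions into measurable and non-measurable. The minimum sizes there are given for CT, calipers and chest X-ray. There is no MRI or CNS threshold, although brain lesions must be assessed by MRI. The general rule is "Non-measurable lesions include small lesions (longest diameter <10 mm".

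Appendix 3 then defines one target list for the whole body: "All measurable lesions up to a maximum of 2 lesions per organ and up to 5 in total and representative of all involved organs". Of the rest it says "All other lesions (or sites of disease) should be identified as non-target lesions", and of non-target lesions that "they need not be measured and instead should be assessed only qualitatively". The definition of partial response is "PR: at least a 30% decrease in the sum of diameters of target lesions".

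Two other places treat small brain lesions differently. Protocol 7.1 requires gadolinium MRI of CNS lesions "with contingent slices of 1 mm for lesions 5 mm to 10 mm in size". SAP 5.2.5 lists as measurable "CNS lesions with longest diameter ≥5 mm provided by gadolinium contrast enhanced" MRI with 1 mm slices, but its opening sentence restricts the list to target lesions identified at baseline.

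IC-ORR (Protocol 9.4.2, SAP 3.2.2) looks only at intracranial lesions and is divided by all participants with CNS metastases at entry, measurable or not. SAP 6.2.2 handles intracranial response like overall response. Neither document defines an intracranial target list, baseline sum or response table.

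**The concern.** Intracranial activity is named in the secondary objective, and IC-ORR and IC-DoR are two of the four secondary endpoints. Whether a shrinking 8 mm brain metastasis can count as a response depends on which passage a site follows. If the site follows Appendix 3, the lesion is non-target and need not be measured, and the SAP cannot recover a diameter that was never recorded. Sites that read the passages differently would produce IC-ORR data that are not comparable.

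The only intracranial benchmark in the protocol, 55.6%, comes from patients with at least one measurable brain lesion. The planned IC-ORR has a wider denominator, so a lower figure could reflect lesion classification rather than drug activity.

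**Working it through.** **Documents' own figures.** The protocol gives no design figure for IC-ORR. Its one precision statement concerns AE rates: √(0.5 × 0.5/100) = 0.05, as stated. The intracranial benchmark also reproduces: 5/9 = 55.6%, with exact (Clopper-Pearson) 95% limits of 21.2% and 86.3%.

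**Step 1: who can have an intracranial PR under Appendix 3.**
- A lesion under 10 mm is non-measurable, so it cannot be a target.
- Non-target lesions are scored only as CR, Non-CR/Non-PD or PD.
- In Table 5 every row that ends in PR starts from CR or PR in target lesions.
- With only intracranial lesions considered, a participant with no intracranial target lesion therefore has no route to PR.
- A participant with at least one brain target lesion can still have PR while other brain lesions are non-target, provided none progresses and no new lesion appears.

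A participant can lack an intracranial target because all brain lesions are under 10 mm, because the shared list was filled elsewhere, or because the brain lesions were previously irradiated. Appendix 3 usually treats irradiated lesions as non-measurable unless they have progressed, and Protocol 4.2 allows prior brain irradiation after a washout.

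**Step 2: whether the SAP repairs this.** The 5 mm rule in SAP 5.2.5 applies to lesions already identified as targets. SAP 6.2.1 takes best response from the investigator's reported time-point responses. Neither turns a non-target lesion into a target.

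**Step 3: whether adopting the 5 mm threshold is enough.** SAP 5.2.7 enters 5 mm for a lesion too small to measure. For a sole intracranial target of baseline diameter d, the decrease in the sum is (d − 5)/d:

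| Baseline d (mm) | Decrease | Reaches 30% |
|---|---|---|
| 5 | 0% | no |
| 6 | 16.7% | no |
| 7 | 28.6% | no |
| 8 | 37.5% | yes |
| 9 | 44.4% | yes |

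The boundary is 5/0.7 = 7.14 mm. Below it, PR needs an actual recorded value under 5 mm.

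**Step 4: complete response.** Disappearance of non-target brain lesions can still be a CR. However, SAP 5.2.8 makes measurable disease part of an adequate baseline, and SAP 3.2.2 counts an inadequate baseline as non-response. The SAP does not say whether the measurable disease must be intracranial for IC-OR. If it must, an intracranial CR would not count for these participants either.

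**Step 5: illustration of size.** Let f be the share of CNS participants with no intracranial target and c their intracranial CR rate. Assume that 55.6% would respond in every group if all lesions were measured. Then reported IC-ORR = (1 − f) × 55.6% + f × c.

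| f | c = 0 | c = 20% |
|---|---|---|
| 10% | 50.0% | 52.0% |
| 20% | 44.4% | 48.4% |
| 30% | 38.9% | 44.9% |
| 40% | 33.3% | 41.3% |

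With an assumed 50 CNS participants, the Wilson 95% interval is 42.3% to 68.8% at f = 0 (28/50) and 22.4% to 47.8% at f = 40%, c = 0 (17/50, rounded from 16.7). Neither f, c nor the number of CNS participants is given in the documents.

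**The case against.** The strongest reply is that the documents disagree rather than exclude small brain lesions. Protocol 7.1 prescribes thin slices for them, SAP 5.2.5 accepts them, and Protocol Section 9 and SAP Section 2 let the SAP modify protocol plans. The CRF and any imaging instructions, which might settle the matter, are not among the documents. This stands as a limit on the claim: how sites will in fact classify these lesions is unknown. It does not remove the need to reconcile the passages, because the SAP cannot supply measurements that were not taken.

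A reader might also infer that any brain lesion left off the target list loses its chance of PR. That is not supported. Response is scored per participant, and one brain target lesion is enough. Appendix 3 also asks for targets that represent all involved organs, so omission of a brain lesion of 10 mm or more is less likely, mainly a matter of disease in more organs than the five places can cover. That clause cannot help lesions under 10 mm, which are ineligible.

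It is fair to add that a separate intracranial list is a method the plan never promised, that the primary endpoint is AE incidence with no hypothesis test or decision rule, and that the benchmark rests on 9 patients. All the illustrative rates lie within its interval.

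**Conclusion.** The inconsistency is real and should be resolved. If sites apply Appendix 3, participants with no intracranial target lesion cannot have an intracranial PR but remain in the denominator. That lowers IC-ORR relative to what Protocol 7.1 and SAP 5.2.5 appear to intend, and keeps those partial responders out of IC-DoR. Participants with at least one brain target are not affected.

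A reader might take the illustration as a forecast loss. The documents do not support one: they do not give the affected share or its CR rate, and the 55.6% comes from patients with measurable brain lesions, whose response rate need not apply to small or unselected ones. Only the direction is supported, and only on the condition that sites follow Appendix 3. No size for any effect on IC-DoR can be given.

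**What to change.** 1. Put the CNS threshold of SAP 5.2.5 (5 mm or more on gadolinium MRI with 1 mm slices) into Appendix 3, so that it agrees with Protocol 7.1. State whether it also applies to overall RECIST and to the adequate-baseline rule, or only to the intracranial endpoints. SAP 5.2.5 currently feeds the baseline rule for overall ORR through SAP 5.2.8, so this is not neutral by default.
2. For participants with CNS metastases, record intracranial target lesions and their baseline sum for IC-ORR and IC-DoR, and refer SAP 6.2.2 and 6.2.4 to them.
3. Adapt the 5 mm imputation in SAP 5.2.7 for CNS targets. Otherwise, lesions below about 7.1 mm at baseline that become too small to measure cannot show a 30% decrease.
4. State whether the measurable-disease requirement in SAP 5.2.8 is intracranial for IC-OR. Also report IC-ORR in participants with measurable CNS disease, which is the basis of the cited 55.6%.

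The cost is a protocol clarification, matching SAP edits, one CRF field or page and slightly more lesion recording per CNS participant. No scans are added, because brain MRI is already scheduled at screening and every 12 weeks. The change needs to be in place before baseline lesions are classified.
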